- I The ABPM **device** is attached on the mornings of Visit 2.2, 5.1 and 7.1 before medication intake for measuring ABPM. This also applies to visits for repeat ABPM testing if required. Patients must have a successful completion of V2.2 ABPM prior to randomisation. Do NOT contact IRT system or dispense randomised study drug until after a successful 24-hour ABPM is complete. If after two attempts a successful reading is not achieved at either Visit 5.1 or Visit 7.1, patients should continue with the next scheduled visit (Visit 5.2/Day 85 or Visit 7.2/Day 169 respectively).
In case the ABPM must be repeated, the patient should continue taking trial medication. If possible, ABPM should take place within the visit window in the [Flowchart](#). If two doses of study medication are taken when the monitor is attached, then the ABPM should be repeated.

At the conclusion of each attempt, patient should be allowed to rest for at least 15 minutes after removal of the ABPM and a trough seated blood pressure measurement should be taken prior to intake of study medication.

- L Instruction and handover of device at Visit 2.1. Daily measurements during Run-in and Follow-up should be performed. During the treatment period, a weekly test is recommended. During the whole trial participation, additional measurements should be done in case of hypo- or hyperglycemia related symptoms.
- M At all visits the respective kit number has to be allocated to the patient via an interactive response technologies (IRT) system. All visit activities must be completed before contacting IRT.
- N At Visit 4 all patients will be dose escalated through an IRT system.
- O Visit 6 will be conducted as a phone visit.

- Q All visit activities must be completed and continued eligibility for randomisation or dosing confirmed prior to using IRT.
- R At Visit 2.1 the food log is dispensed only and to be completed for three consecutive days prior to Visit 3.

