Phase III studies have shown that treatment with empagliflozin 10 mg or 25 mg for up to 24-weeks results in a reduction of HbA1c up to 0.85%, body weight up to 2.2kg and SBP up to 4.8 mmHg compared to placebo. This was observed with empagliflozin monotherapy, add on to metformin, to metformin plus sulfonylurea, to pioglitazone with or without metformin, and to basal insulin with metformin and/or sulfonylurea [c01678844]. Since the observed effect on BP is greater with 25 mg compared with 10 mg empagliflozin, the study design will include a dose escalation from a starting dose of 10mg to 25 mg empagliflozin 4 weeks after the start of treatment. The placebo-controlled design is considered ethically acceptable on the basis of appropriate criteria for patient discontinuation, relatively short study duration and criteria for rescue therapy as defined in the relevant guidelines (e.g. FDA Guidance for Industry for developing drugs in diabetes) (refer to [Section 2.3](#)).

This study will also provide a better understanding of the effect of empagliflozin on the circadian patterns of 24-hour BP control in hypertensive black/African American patients with T2DM. ABPM is considered a gold standard in BP measurement and a better predictor of cardiovascular risk than clinic BP ([P13-12437](#)). The use of ABPM has been integrated in major hypertension guidelines such as JNC8 ([R14-0310](#)) and European Society of Hypertension / European Society of Hypertension ([P13-12437](#)) and the American Heart Association ([P08-03352](#)). While slight differences exist among these guidelines there is agreement that ABPM provides a more accurate measurement of BP and correlates with hypertension related organ damage more closely than office BP, provides a more accurate evaluation of “white coat” as well as masked hypertension and a more accurate assessment of patients with drug resistance and hypotensive symptoms ([P08-03352](#), [P13-12437](#)).

The randomised period is planned for 24 weeks to reflect both changes in HbA1c (primary endpoint) and ABPM and body weight (key secondary endpoints). The two-week follow-up period is considered to be sufficient, as previous studies with empagliflozin have shown that the pharmacodynamic effect of empagliflozin only extends to about 3 days after the last dose.

The rationale for dose and dose-interval selection is described in [Section 4.1.3](#).

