5.2.5 Assessment of other safety parameters

All patients will be provided with HBGM equipment and supplies for use at home during the 2-week Run-In Period. Instruction on the proper use of the HBGM will be provided by the study staff. The patient will be asked to record the results of the HBGM test on a HBGM Testing Log that will be included in the patients source document file. Only in the case of linked adverse events or of hypoglycemia, the single HBGM values will be recorded in the CRF. The respective procedure for illiterate patients (if included) is described in the [Appendix 10.1](#). Even though review of the HBGM log is required, electronic review of the

Proprietary confidential information.

[figure not shown]
© 2016 Boehringer Ingelheim International GmbH or one or more of its affiliated companies. All rights reserved.

This document may not - in full or in part - be passed on, reproduced, published or otherwise used without prior written permission.

glucometer is not required. If a patient forgets to return their Log, they should be reminded to record HBGM values on the Log and return it at the next visit.

During Run-In and Follow-up, HBGM testing should be performed once daily in the fasted state and at any time the patient is symptomatic, i.e., experiences signs/symptoms of hyper- or hypoglycemia. If during Run-in, results of a HBGM test reveal blood glucose of >270 mg/dl (>15.0 mmol/L) after an overnight fast the patient should contact the site. Patient should also eat or drink something immediately and contact the site in the event that blood glucose level drops below 54 mg/dl (3.0 mmol/l). The investigator should then decide about start of the randomised period or further patient participation in the trial based on fasted plasma glucose determinations according to the inclusion and exclusion criteria as outlined in [Section 3.3](#).

[figure not shown]
During the randomised treatment period, HBGM testing should be performed once weekly (more frequently if required by local authorities) and at any time the patient is symptomatic, i.e., experiences signs/symptoms of hyper- or hypoglycemia. If during this period, results of a fasting HBGM test reveal blood glucose levels meeting rescue criteria (see [Section 4.2.1](#)), the patient should contact the site and the investigator should follow the instructions given in Section 4.2.1.

Proprietary confidential information.

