- If ABPM was successful, procedures for Visit 7.2 can be conducted on the same day after the ABPM device is removed and trough seated blood pressure measurement is taken. If done on the same day, procedures for Visit 7.2 should be done prior to administering study medication.
- If the first ABPM attempt was unsuccessful (failed QC), a repeat reading should be taken within 2 days. Patient having two technically unsuccessful ABPM sessions may continue with Visit 7.2. Procedures for Visit 7.2 can be conducted on the same day after the ABPM device is removed and trough seated blood pressure measurement is taken.
- Allow the patient to rest for at least 15 minutes after the monitor is removed. Then take a seated blood pressure measurement. Record the time of this measurement. This should be done prior to administering study medication.
- Administer dose of study medication.
- For further instructions for ABPM measurements, please see [Section 5.1.2](#).
- Instruct patients NOT to take study medication on the morning of the next trial visit.

Visit 7.2 (end of treatment)

- BP measurement and orthostatic blood pressure test should always be done before taking any blood samples.

Proprietary confidential information.

© 2016 Boehringer Ingelheim International GmbH or one or more of its affiliated companies. All rights reserved.

This document may not - in full or in part - be passed on, reproduced, published or otherwise used without prior written permission.

- Collection of urine and blood for laboratory testing.
- PK trough sample should be collected.
- Collect returned medication.
- Patients should be reminded about the importance of following the agreed diet and exercise plan.
- Provide HBGM equipment/supplies and instruct patient on the correct use of HBGM.
- Instruct patient to perform a HBGM test at least once daily during the follow up period. Instruct patient to immediately perform a blood glucose test if they experience signs/symptoms of hypo- or hyperglycemia. Instruct patient to contact site immediately if blood glucose reaches limit described in [Section 4.2.1](#).
- Visit 7.2 is the last visit of the treatment period after ABPM is done. No study medication is administered at this visit.
- Instruct patient to continue to take the current therapy as usual. Additional antidiabetic medication can be started after the follow-up visit, in case there is no medical need for rescue medication before that.

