7.8.1.1 Assignment of AEs to treatment

The analysis of AEs will be based on the concept of treatment-emergent AEs. This means that all AEs occurring between first drug intake until 7 days after last drug intake will be assigned to the first treatment received. All AEs occurring before first drug intake will be assigned to 'pre-treatment' and all AEs occurring after last drug intake + 7 days will be assigned to 'post-treatment'.

In general, in-text AE tables will only present AEs assigned to the first treatment taken, except drug-related AEs, which will be presented as actual treatment taken at each given timepoint. End-of-text tables will display, in addition, AEs observed 'pre-treatment' (including AEs observed during screening and placebo run-in regardless of treatment group). Appendix 16.1.9.2 will include an analysis where AEs and serious AEs (SAEs) are assigned to the following phases: Screening, placebo run-in, each treatment group, post-treatment for each treatment group.

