7.8.1.4 Analysis of hypoglycaemic events

The investigator will record for each AE whether it represents a hypoglycaemic AE and, if so, record additional information to assess the intensity of the hypoglycaemic AE. On the basis of this information the hypoglycaemic AE will be classified as:

- asymptomatic hypoglycaemia: event not accompanied by typical symptoms of hypoglycaemia but with a measured plasma glucose concentration < 3.0 mmol/L (< 54 mg/dL),
- documented symptomatic hypoglycaemia with a measured plasma glucose concentration ≥ 3.0 mmol/L and ≤ 3.9 mmol/L (≥ 54 mg/dL and ≤ 70 mg/dL): event accompanied by typical symptoms of hypoglycaemia,
- documented symptomatic hypoglycaemia with a measured plasma glucose concentration < 3.0 mmol/L (< 54 mg/dL): event accompanied by typical symptoms of hypoglycaemia but no need for external assistance,
- severe hypoglycaemic episode: event requiring the assistance of another person to actively administer carbohydrate, glucagon or other resuscitative actions.
- symptomatic hypoglycaemia and plasma glucose concentration > 3.9 mmol/L (> 70 mg/dL)
- symptomatic hypoglycaemia and plasma glucose concentration not measured

Asymptomatic hypoglycaemia with a measured plasma glucose concentration ≥ 3.0 mmol/L and ≤ 3.9 mmol/L (≥ 54 mg/dL and ≤ 70 mg/dL) will also be recorded by the investigator but will not be regarded as an AE.

The number of patients with hypoglycaemic AEs or non-AEs according to investigator's judgement will be tabulated by treatment group. A subgroup analysis of confirmed hypoglycaemic AEs with respect to age category, antidiabetic rescue therapy and renal function will be performed. Confirmed hypoglycaemic AEs are defined as hypoglycaemic AEs according to investigator's judgement confirmed with plasma glucose concentration ≤ 3.9 mmol/L (≤ 70 mg/dL) or required assistance.

The impact of treatment on the occurrence of hypoglycaemic AEs will be explored using logistic regression with model involving treatment, renal function, pretreatment with metformin and continuous baseline HbA_{1c}. Time to the onset of the first hypoglycaemic AE will be analysed by Kaplan-Meier estimates. The logistic regression and Kaplan-Meier analysis will be performed on confirmed hypoglycaemic AEs.

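### Scheduled home glucose testing goes from weekly to daily while AEs still count as on-treatment, so asymptomatic hypoglycaemia is found more often just after drug stop; the effect is minor and merits a supplementary analysis

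*Protocol*

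**What the plan says.** **Testing schedule.** Protocol Flow Chart, footnote L: "Daily measurements during Run-in and Follow-up should be performed. During the treatment period, a weekly test is recommended". Protocol 5.2.5 agrees. On randomised treatment, "HBGM testing should be performed once weekly (more frequently if required by local authorities) and at any time the patient is symptomatic"; outside it, "During Run-In and Follow-up, HBGM testing should be performed once daily in the fasted state". For completers the switch comes at Visit 7.2 (protocol 6.2.2): "Instruct patient to perform a HBGM test at least once daily during the follow up period". The same section says that no trial drug is given at that visit. Testing for symptoms follows one rule in all periods: "During the whole trial participation, additional measurements should be done in case of hypo- or hyperglycemia related symptoms".

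**Analysis window.** SAP 7.8.1.1: "all AEs occurring between first drug intake until 7 days after last drug intake will be assigned to the first treatment received". SAP Table 6.7: 1 and protocol 5.2.2.2 and 7.3.3 give the same 7 days.

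**Hypoglycaemia analyses.** SAP 7.8.1.4 plans a logistic regression, a descriptive event rate and a time-to-event display: "Time to the onset of the first hypoglycaemic AE will be analysed by Kaplan-Meier estimates". The regression and the Kaplan-Meier analysis use confirmed hypoglycaemic AEs. Another table pools events recorded as AEs and as non-AEs. No hypoglycaemia-specific window is given.

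**Duration of effect.** Protocol 3.2 justifies the two-week follow-up by stating that the "pharmacodynamic effect of empagliflozin only extends to about 3 days after the last dose".

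**The concern.** The two rules meet in the week after the last dose. Patients are then asked to test about seven times as often as they did on drug, and whatever they find is still labelled on-treatment. An asymptomatic low value is found only if someone tests, so more such events will be found in that week whatever the drug does.

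Three outputs are exposed:

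- The on-treatment event rate is inflated in both arms.
- The Kaplan-Meier curve can show a late step that reflects testing frequency.
- The by-phase AE tables planned in SAP 7.8.1.1 compare run-in and post-treatment periods with daily testing against a treatment period with weekly testing.

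If empagliflozin does raise hypoglycaemia, the extra events from days without drug effect also pull the arm ratio for schedule-detected events towards 1.

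The database cannot correct this later. Under protocol 5.2.5, single home readings enter the CRF only when linked to an adverse event or to hypoglycaemia, so the number of tests per patient is not available as a denominator. Dates and times of low values are recorded (protocol 5.2.3), so a split by window is feasible.

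**Working it through.** The documents give no hypoglycaemia rate and no test count, so there is no planned figure to reproduce. The inputs below come from the documents unless marked as assumptions.

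**Test counts for an on-schedule completer**

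- Visit 7.2 is Day 169 and no dose is given, so the last dose is on Day 168.
- Weekly tests on drug: 168/7 = 24.
- The on-treatment window ends on Day 168 + 7 = Day 175. Daily tests on Days 170-175: 6.
- Share of scheduled tests after drug stop: 6/(24 + 6) = 20%. Share of time: 7/175 = 4%. With 23 or 24 weekly and 6 or 7 daily tests, the test share is 20-23%.
- The stated 3-day effect runs to Day 171. Tests on Days 172-175 fall after it: 4/30 = 13%.

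**Arm ratio for schedule-detected events**

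Assumptions: the per-test risk is RR times placebo through Day 171 and equal between arms afterwards. RR is assumed, because the documents give none.

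Observed ratio = (26·RR + 4)/30, where 26 = 24 weekly tests + the tests on Days 170 and 171. Log-scale loss = 1 − ln(observed)/ln(RR).

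| True RR | Observed | Log-scale loss |
|---|---|---|
| 1 | 30/30 = 1.00 | none |
| 1.5 | 43/30 = 1.43 | 11% |
| 2 | 56/30 = 1.87 | 10% |
| 3 | 82/30 = 2.73 | 8% |

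**Event rate for schedule-detected events**

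The window is 175 days, or 25 weeks. Set the placebo rate on drug at 1 per week. Placebo becomes 30/25 = 1.20, which is 20% too high. The active arm at RR 2 becomes 56/25 = 2.24 against 2.00, which is 12% too high. The difference in counts does not shrink: 26·RR + 4 − 30 = 26·(RR − 1), against 24·(RR − 1) on drug.

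**Mixed endpoint**

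Symptomatic events are found at the same intensity throughout. Let m be the share of on-drug events that are schedule-detected (assumption).

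- Placebo count: 24 + 6m + (1 − m).
- Active count: 24·RR + m·(2·RR + 4) + (1 − m)·(3·RR + 4)/7.
- At RR 2 and m = 0: 49.43/25 = 1.98.
- At RR 2 and m = 0.1: 50.09/25.5 = 1.96.
- At RR 2 and m = 0.5: 52.71/27.5 = 1.92.

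In the confirmed-AE endpoint, m covers only asymptomatic values below 54 mg/dL. SAP 7.8.1.4 does not regard asymptomatic values of 54-70 mg/dL as AEs.

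**After a cut at last intake + 3 days**

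The window then holds 26 tests in 171 days. Under the same assumptions the observed ratio equals RR. The placebo rate is 26 × 7/171 = 1.06 per week, so the inflation falls from 20% to about 6%.

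**The case against.** The case against giving this much weight is strong, and most of it stands.

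- Testing is identical in the two arms. A reader might infer that the arm contrast is diluted regardless. The documents do not support that: at RR 1 nothing moves, and the effect is confined to ratio scales. Protocol 2.3 reports only a slightly higher incidence on sulfonylurea or insulin background and gives no ratio.
- A reader might treat all six daily tests as free of drug effect. That gives (24·RR + 6)/30, or 1.40, 1.80 and 2.60, a loss of 13-17%. This conflicts with the 3-day effect in protocol 3.2, which covers two of the six tests.
- The regression and Kaplan-Meier analysis use confirmed AEs, and symptomatic and severe events are AEs whatever the testing schedule (protocol 5.2.3). The larger effect falls on the table pooling AEs and non-AEs.
- The completer count is not general. Weekly testing is a recommendation and may be more frequent. Under protocol 6.2.3, early stoppers may have their discontinuation visit 7 days or more after the last dose, so their window may contain few instructed daily tests. They may, however, start a new antidiabetic regimen at once, which is a separate reason to show these days apart.
- SAP 7.8.1.4 already classifies events as asymptomatic, symptomatic or severe, so part of the separation exists. What is missing is a split by time since last dose and a by-phase presentation that uses those classes.

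**Conclusion.** The point holds in a limited form. The increase in scheduled testing while events still count as on-treatment follows directly from the protocol and SAP. For a completer it puts 20% of the scheduled tests into 4% of the time, and 13% after the stated drug effect. This inflates the detection of asymptomatic events in both arms and can add a late step to the Kaplan-Meier curve through asymptomatic values below 54 mg/dL.

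The pull on the ratio for schedule-detected events is conditional: 8-11% on the log scale at assumed ratios of 1.5 to 3. It rests on equal per-test risk between arms after Day 171, full effect until then, and testing as scheduled. For an endpoint with 10-50% schedule-detected events, an assumed ratio of 2 becomes 1.96-1.92.

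A reader might conclude that the main hypoglycaemia window should be cut to last dose + 1 day, as Table 6.7: 1 does for FPG. The documents do not support that. It would drop events on days when protocol 3.2 says the drug still acts, and it would depart from the protocol's treatment-emergent definition.

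Severity is minor. Protocol 7.3.3 makes the safety analyses descriptive with no hypothesis testing, so no confirmatory result is touched.

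**What to change.** Keep the 7-day window for the main AE and hypoglycaemia tables. Then, before unblinding:

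1. In SAP 7.8.1.4, add a supplementary hypoglycaemia analysis (logistic regression, event rate and Kaplan-Meier) with events cut at last intake + 3 days.
2. Show events in the remaining residual days (days 4-7 after last intake) in a separate column.
3. In the by-phase tables of SAP 7.8.1.1, show asymptomatic hypoglycaemia apart from symptomatic or severe events. Add a footnote that scheduled testing was daily in run-in and follow-up and weekly on treatment.

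The cost is SAP wording and minor programming. It needs no new data and no change to the testing schedule or to patient care. The cut does not remove the testing step entirely, since two daily tests stay inside the 3 days, so the footnote is still needed.

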ICH	International Conference on Harmonisation
IEC	Independent Ethics Committee
IPV	Important Protocol Violation
IRB	Institutional Review Board
IRT	Interactive Response Technologies
ISF	Investigator Site File
IUD	Intra Uterine Device
IUS	Intra Uterine System
JNC8	Eighth Report of the Joint National Committee on Prevention, Detection, Evaluation, and Treatment of High Blood Pressure
kg	kilogram
LDH	Lactate Dehydrogenase
LDL	Low Density Lipoprotein
LOCF	Last Observation Carried Forward
m ²	Meters squared
MedDRA	Medical Dictionary for Drug Regulatory Activities
mEq/L	milliequivalents per litre
mg	milligrams
mg/dl	milligrams per decilitre
min	minutes
mL	millilitres
mmol/l	Millimoles per litre
MMRM	Mixed Model Repeated Measure
Na ⁺	Sodium
NAFLD	Non-alcoholic Fatty Liver Disease
nM	nanomoles
nmol/L	nanomoles per litre
NOAEL	No Observed Adverse Effect Level
OPU	Operative Unit
p.o.	per os (oral)
PG	Pharmacogenomics
PK	Pharmacokinetics
PPS	Per Protocol Set
PTD	Premature Treatment Discontinuation
RBC	Red Blood Cells
RDC	Remote Data Capture
REP	Residual Effect Period
SAE	Serious Adverse Event
SBP	Systolic Blood Pressure
SGLT-2	Sodium-Glucose Co-Transporter-2
SGOT	Serum Glutamic Oxaloacetic Transaminase
SGPT	Serum Glutamic Pyruvate Transaminase

Proprietary confidential information.

© 2016 Boehringer Ingelheim International GmbH or one or more of its affiliated companies. All rights reserved.

This document may not - in full or in part - be passed on, reproduced, published or otherwise used without prior written permission.

SOP	Standard Operating Procedure
STEMI	ST Wave Elevated Myocardial Infarction
SU	Sulfonylurea
SUSAR	Suspected Unexpected Serious Adverse Reaction
T2DM	Type 2 Diabetes Mellitus
TCM	Trial Clinical Monitor
TMF	Trial Master File
TSAP	Trial Statistical Analysis Plan
TSH	Thyroid Stimulating Hormone
ULN	Upper Limit of Normal
UTI	Urinary Tract Infection
WBC	White Blood Cells

Proprietary confidential information.

© 2016 Boehringer Ingelheim International GmbH or one or more of its affiliated companies. All rights reserved.

This document may not - in full or in part - be passed on, reproduced, published or otherwise used without prior written permission.

1. INTRODUCTION

Empagliflozin is an orally available inhibitor of the sodium-glucose co-transporter 2 (SGLT-2), that promotes enhanced glucose excretion in the urine, thereby lowering blood glucose concentrations in patients with type 2 diabetes mellitus (T2DM).

